3.1 Cohort Creation and Characterization

Population and setting: All children who present to pediatric nephrology clinics with a clinical diagnosis of nephrotic syndrome will be eligible for enrollment into the longitudinal cohort. All pediatric nephrology centres in Canada (n=13) are participating in this national study (see attached support letters). All pediatric nephrologists who care for children with nephrotic syndrome in Canada are eligible for enrollment.

Enrollment period: The enrollment period for the prospective cohort will last 4.0 years. The observation period will continue for an additional 6 months after the enrollment period (to ensure minimum 6 months follow-up for all patients by end of study).

Inclusion criteria: A patient is eligible to enter the cohort if he/she meets one of the following 2 criteria. See Appendix, Figure 1 for patient enrollment plan.

- A child with **first presentation** of nephrotic syndrome who meets the following criteria: age 1 to ≤17.5 years; edema present; urinalysis shows proteinuria (> 3+ on dipstick; > 3 g/L on urinalysis or urine protein to creatinine ratio > 200 mg/mmol); serum albumin < 25 g/L; and no prior treatment with steroids.
- A child with an established diagnosis of childhood nephrotic syndrome who presents at the beginning of either a **first or second relapse** (defined as proteinuria > 3+ on dipstick, > 3g/L on urinalysis or urine protein to creatinine ratio > 200 mg/mmol for 3 consecutive days) during enrollment period, prior to start of steroid sparing agents or kidney biopsy.

[figure not shown]
Exclusion criteria: Patients will be excluded if they meet one of the following criteria either at enrollment or during course of study: 1) secondary cause of nephrotic syndrome (e.g. lupus, malignancy); 2) C3 low suggesting high likelihood of secondary cause of nephrotic syndrome. Patients ultimately shown to be steroid resistant will be excluded from the final analysis, but will continue to be followed in the prospective cohort. Enrolled patients who turn 18 years of age during the study will exit the study. Further follow-up will be sought for these adult patients using a revised ethics application.

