Patient enrollment: Two team members from each participating site will be primary contacts for the study (one physician and one nurse/research staff). Every 2 weeks these individuals will generate a list of patients seen with nephrotic syndrome by reviewing inpatient and outpatient data (clinic scheduling records) to determine eligibility. All patients with a clinical diagnosis of nephrotic syndrome who meet the inclusion and exclusion criteria will be introduced to the study by the primary treating physician. The site investigator will approach patient/parents to obtain informed consent and will also obtain assent from older patients (age >12 years). Patients will be enrolled in the study if they meet inclusion criteria and

their legal guardian has given informed consent. Consent forms will be available in English and French. Logs of all patients screened and consented, and for those who declined the reason will be kept.

Physician enrollment: Informed consent will be obtained from physicians within participating nephrology care teams to allow their demographic information (age, gender, location of nephrology training, years in practice) to be collected. Physician data will be linked to their patient's data in the nested data architecture. Once linked, physician identifying information will be removed. If a consenting patient's physician declines to participate in the study, the patient's data will be linked to a generic category of 'unknown physician.'

Patient data being collected: Study data will be collected at the following study points (see Figure below and more details shown in Appendix, Figure 2): 1) study entry (whether first presentation, first relapse or second relapse); 2) at the beginning of all subsequent relapses [defined as proteinuria > 3+ on dipstick, > 3g/L on urinalysis or urine protein to creatinine ratio > 200 mg/mmol for 3 consecutive days or start of full dose steroids (60 mg/m² or 2mg/kg)]; 3) at the end of first presentation and end of all subsequent relapses [defined as both remission of proteinuria – negative or <1.0 g/L protein on dipstick for 3 consecutive days, and off steroids]; 4) study visits every 6 months after entry; 5) at start of all steroid sparing agents; 6) at time all kidney biopsies; and 7) study end.

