At entry, we will record demographic information (age, gender, ethnicity, family income, parental education, past medical history), height, weight, blood pressure, blood test results (C3, albumin, cholesterol, creatinine), urine protein values by dipstick (routine clinical practice is to use urine albumin dipsticks [Albustix™, Bayer], but urine protein to creatinine ratio will be recorded if available), medical history and details of steroid prescription. For patients entering at first or second relapse, demographic and treatment information regarding first presentation and/or first relapse will be collected using retrospective chart review when available. We will allow for enrollment up to second relapse (lengthening time interval to obtain consent) in order to maximize patient recruitment. Standardized assessments by physicians will be performed at the following study points: study entry, semi-annual study visits, and at study end.

Data for study points will be obtained using one or all of the following methods: chart review, reviewing patient log books of daily home urine protein measurements and steroid dose given, and phone calls to family to confirm details of clinical course (including date of proteinuria remission for each relapse). Logs maintained by patients are part of routine clinical care in nephrotic syndrome; all study patients will be provided with standardized log books for medications and relapse tracking. This schedule and method of assessments for study points were designed to mirror routine clinical care (as reported by most sites) and to maximize feasibility while maintaining ongoing engagement by study patients and physicians.

Defining an episode of treatment: As nephrotic syndrome is a relapsing and remitting disease, a significant portion of the study data will involve documenting treatment for both first presentation and

relapses of nephrotic syndrome (called ‘episodes’ in this study). Detailed steroid prescription information will be recorded at entry, and at the beginning and end of all subsequent episodes.

An **episode** is defined as the time from start of full dose steroid therapy (60 mg/m² or 2mg/kg) to cessation of steroids or re-start of full dose steroids as in steroid dependent patients who relapse while tapering steroids.

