Privacy and confidentiality: We will assign unique study numbers to patients, physicians and centres – to protect anonymity of all participants and centres. All identifying information will be securely stored at individual sites and will not be shared with central study staff.

Characterizing the cohort: We will describe (using means with standard deviation, medians with interquartile range and proportions as appropriate) the cohort demographics, and all outcomes of interest by centre-, physician, and patient- level variables. We will describe the following outcomes: overall steroid prescribed (total dose and number of treatment days), time to first relapse, relapse rate during observation, time to steroid sparing agents, choices of steroid sparing agents and indication, time to kidney biopsy, reasons for biopsy, complications of steroid therapy. Outcomes related to complications of steroid treatment will include: anthropometric changes during observation period (age- and sex-specific standard-deviation scores (z scores) for height, weight, and body-mass index); persistent systolic/diastolic blood pressure $\geq 95^{\text{th}}$ percentile during observation period [yes/no] and requirement for antihypertensive therapy [yes/no] and duration of therapy; and external manifestations of steroid toxicity evident during semi-annual study visits (Cushingoid faces [yes/no], hypertrichosis [yes/no], cataracts [yes/no], striae [yes/no], acne [yes/no]). Definitions of external manifestations of steroid toxicity are

similar to those observed in prior nephrotic syndrome steroid dosing studies.³⁸ See Appendix, Table 4 for detailed description of these variables.

3.2 Work plan for objective 1

Design: To determine the association of steroid dose prescribed with relapse rates, we will use the prospective cohort as described in section 3.1. We hypothesize that increasing steroid dose prescribed per unit time will be associated with decreasing relapse rates. All patients with steroid sensitive nephrotic syndrome enrolled into the prospective cohort will be eligible for this study. The observation period will span a maximum of 4 years and minimum of 6 months. Figure 4 in the Appendix provides a visual representation of the outcome and exposure as defined below for this objective.

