Outcome: The primary outcome of interest is relapse rate (number of relapses/per person unit time). Relapse rate is the most clinically relevant outcome for nephrotic syndrome and the best indicator of morbidity experienced by patients; this outcome definition is consistent with prior literature in this area.⁴⁰

Exposure: The exposure is steroid prescribed per unit time - that is the total dose patients were prescribed as treatment for episodes of proteinuria divided by the sum of duration of 'days on steroids' during observation period. Days on steroids is defined by the sum of the length in days of all episodes (see definition of episode in section 3.1, also graphically represented in Appendix Figure 4) observed. This definition is consistent with measures of steroid exposure used in prior nephrotic syndrome steroid dosing studies conducted in Europe and in a Canadian study of steroid associated osteoporosis in children.^{38,55} Systemic steroid exposure (both oral and intravenous) will be converted into prednisone equivalents (mg/m^2) using standard dose conversion tables and weight based dosing criteria [mg/kg] will be converted to mg/m^2 .

Analysis plan: The unit of analysis is the patient. Given that the main outcome of interest is relapse rate, we will use Poisson regression models with steroid prescribed per unit time as the exposure and relapse rate per unit time as the outcome, adjusting for patient level variables (age, gender, ethnicity, household income, parental education) and episode at entry into study (either first presentation, first relapse or second relapse), and taking into account time at risk. We are not using multi-level (hierarchical) analysis in this objective, as there is no clustering at the patient-level. There is only one measurement per patient, relapse rate adding all episodes experienced by one patient as a count.

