Feasible sample and power considerations: We estimated a feasible sample based on data gathered from 2 sources: an ongoing longitudinal study of children with nephrotic syndrome (INSIGHT study, led by [name]) recruiting a Toronto based cohort,⁵³ and our preliminary data (Appendix Figure 5 for preliminary recruitment rate). Based on the expected consent rate of 72%, and estimated drop out of 10% (due to loss to follow-up or steroid resistance), we estimate that we will be able to enrol and follow, at least, 520 patients over a period of 4.0 years (65 patients every 6 months). In our preliminary work, we have already enrolled 77 patients from 6 sites, thus our total estimated sample is 597 patients.

Although we hypothesize that increasing steroid dose prescribed per unit time will be associated with decreasing relapse rates, no studies to date have reported a specific magnitude of the effect of steroid prescribed per unit time on relapse rates. A systematic review of available clinical trials examining this issue, published in 2007, only reports on risk ratios based on the dichotomous outcome of any relapse at a pre-specified time interval (usually 12 or 24 months).⁴⁰ Our outcome of interest is an actual rate (count of relapses/person years). Hence, a power based, effect size dependent sample size calculation was not performed. At a significance level $\alpha = 0.05$, and under the following assumptions of a mean daily steroid dose of $30.64 \text{ mg}/\text{m}^2$ with a standard deviation (of the dose) of 8.85, a base rate of relapse of 1.68 per person year, average follow up (time at risk of relapse) of 2 years and a conservative correlation (R^2) of the steroid dose with other covariates of 0.2, we would have 90% power to detect an incidence rate

ratio of 0.989 or smaller (i.e. a larger effect size) in a multiple Poisson regression. We are allowing for a 2 tailed test to allow the possibility of the effect being on either side of the null.

3.3 Work Plan for Objective 2

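### In follow-up a full-dose steroid start alone can count as a relapse, so one prescribing decision can enter both the outcome and the exposure of Objective 1; the entry definition has no such route

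*Protocol*

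**What the plan says.** Section 3.1 of the protocol defines a relapse twice.

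- **At entry** (Inclusion criteria), a first or second relapse needs proteinuria above one of three thresholds, ending with "urine protein to creatinine ratio > 200 mg/mmol for 3 consecutive days) during enrollment period". Starting steroids is not an alternative.
- **In follow-up** (Patient data being collected), the thresholds are the same, but the condition is "for 3 consecutive days or start of full dose steroids". Neither proteinuria nor an earlier remission is stated for the steroid route.

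Section 3.1 also says that an episode "is defined as the time from start of full dose steroid therapy" until steroids stop or full dose is restarted.

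The Objective 1 work plan (Section 3.2) builds on these terms. On the outcome: "The primary outcome of interest is relapse rate (number of relapses/per person unit time". The analysis plan describes the count as "relapse rate adding all episodes experienced by one patient as a count". The exposure is total prescribed dose divided by days on steroids, and "Days on steroids is defined by the sum of the length in days of all episodes". The Poisson model adjusts for patient characteristics and for the episode at entry. It has no physician or centre term.

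**The concern.** An outcome should be ascertained independently of the exposure. Here a decision to give full-dose steroids can add one event to the outcome and, at the same time, add dose and days to the exposure.

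Take two children with the same proteinuria lasting one or two days. If one physician starts full dose at once, a relapse is recorded. If another waits and the proteinuria clears, none is. The disease is the same and the counts differ.

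Prescribing habit is what this study expects to vary. Section 4.0 reports variation between sites, between physicians within centres, and between patients of the same physician. If readiness to start full dose goes with mean daily dose, relapse counts will differ by dose for reasons unrelated to any effect of dose. The Objective 1 model has no prescriber-level term to absorb this. The study hypothesis, that "increasing steroid dose prescribed per unit time will be associated with decreasing relapse rates", concerns a small effect per mg/m², so modest differences in counting can matter.

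**Working it through.** **1. The definitions side by side**

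| Use | Three-day proteinuria | Full-dose start alone |
|---|---|---|
| Relapse at entry (3.1) | required | not sufficient |
| Relapse in follow-up (3.1) | sufficient | sufficient |
| Start of an episode (3.1) | not mentioned | defines the start |
| Outcome count (3.2) | through the relapse definition | through relapses, and through episodes added up |
| Exposure (3.2) | not used | starts the days and dose counted |

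The full-dose start is the element that outcome and exposure share.

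**2. The plan's own detectable effect**

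Inputs from Section 3.2: mean dose 30.64 mg/m², SD 8.85, base rate 1.68 per person-year, 2 years of follow-up, R² 0.2, two-sided alpha 0.05, power 90%, rate ratio 0.989, 597 patients. Assumptions: the rate ratio is per 1 mg/m² of daily dose, and 1.68 is the rate at zero dose.

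- b = ln(0.989) = −0.01106
- m = exp(b × 30.64 + b² × 8.85² / 2) = 0.716
- N = (1.960 + 1.282)² / [b² × 2 × 1.68 × m × 8.85² × (1 − 0.2)] = 10.51 / 0.01844 ≈ 570 for 90% power

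At 597 patients the power is 91.3% and the detectable rate ratio is 0.9893, which rounds to 0.989. The plan's figure reproduces. If 1.68 is instead the rate at the mean dose, power is 97.5%. The target is therefore 0.011 from the null per mg/m².

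**3. What the steroid route could do (assumed inputs)**

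Let p be the share of relapses that meet only the steroid route, and s the log-slope of their rate per SD of dose. The documents give neither. If dose has no true effect, then to first order

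spurious rate ratio per mg/m² = exp(p × s / 8.85).

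With s = 0.25, that is, steroid-only starts 1.28 times as frequent per SD of dose (e^0.25):

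- p = 5%: exp(0.0125 / 8.85) = 1.0014
- p = 10%: exp(0.025 / 8.85) = 1.0028
- p = 20%: exp(0.05 / 8.85) = 1.0057

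A simulation agrees. It used 597 patients, 2 years each, confirmed relapses at 1.68 per year unrelated to dose, an unadjusted Poisson model, and 600 runs per setting:

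| Share p | s = 0: rate ratio, rejection | s = 0.25 | s = 0.5 |
|---|---|---|---|
| 5% | 1.000, 6% | 1.0015, 11% | 1.0034, 27% |
| 10% | 1.000, 6% | 1.0028, 24% | 1.0063, 74% |
| 20% | 1.000, 7% | 1.0057, 72% | 1.0126, 100% |

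On the log scale, the s = 0.25 cases are about 13%, 26% and 51% of the target (0.00141, 0.00282 and 0.00565 against 0.01106). With s = 0 there is no bias. With s = −0.25 the same formula gives 0.9986, 0.9972 and 0.9944, in the direction of the hypothesis.

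**4. Does an extra start raise the exposure?**

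Exposure after an added episode is (D₁ + D₂) / (t₁ + t₂), a time-weighted average of the old mean daily dose and that of the new episode. If the two means are equal, exposure does not move. It rises or falls only as the new episode's own mean daily dose, taper included, lies above or below the patient's average. The sign is therefore open.

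**The case against.** The strongest reply is that the steroid route has a sound purpose: it captures relapses treated before three days are recorded. The phrase may even mean proteinuria lasting three days or until treatment begins. It stands in a list of data-collection points, and the appendix table of standard definitions, the data forms and the figure of outcome and exposure were not available. One of them may restrict the steroid route. Children who have not remitted are a narrow case, since steroid-resistant patients leave the final analysis.

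Much of this is fair. Still, the sentence is the only definition of a subsequent relapse in the text available, the episode definition points the same way, and on the milder reading treatment timing still replaces the three-day confirmation.

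Three stronger inferences are tempting, and the documents do not support them.

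- *Practices that treat early lose children who would enter at relapse.* The entry criterion asks for three days of proteinuria, not three untreated days. Section 2.2 says steroid-sensitive patients typically remit within two weeks of therapy, so a child treated on day 1 can still be proteinuric on day 3 and qualify. The same fact limits how many follow-up relapses meet the steroid route alone.
- *The bias must be positive.* Exposure is a mean daily dose, not a cumulative one, so step 4 leaves the sign open.
- *A 10% difference in counting would cancel the detectable effect.* Arithmetically, 0.989^8.85 = 0.907, with inverse 1.103, so 10% more relapses per SD of dose would offset it. But if 10% of relapses are steroid-only, this needs such starts to rise about 2.6-fold per SD (ln 1.10 = 0.0953; 0.0953 / 0.10 = 0.953; e^0.953 = 2.59). Nothing in the protocol suggests that.

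**Conclusion.** The point holds as a fault in the outcome definition. The two relapse definitions in Section 3.1 differ, and the one used in follow-up lets a prescribing decision create the Objective 1 outcome while also feeding its exposure. The rate ratio is biased if steroid-only relapses are related to mean daily dose, and not otherwise.

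Size and direction cannot be determined from the documents. Under the assumed shares of 5% to 20% and a log-slope of 0.25 per SD, the spurious rate ratio is about 1.0015 to 1.006 per mg/m². That is a minor to substantial fraction of the 0.011 distance to the target, and it is an illustration, not an estimate. The point is a worthwhile, inexpensive improvement. It does not show that the analysis fails.

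**What to change.** Reconcile the two definitions for outcome counting only, and state whether the Objective 1 count is of relapses or of episodes.

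1. Record for each follow-up relapse which route it met: three-day proteinuria, full-dose start, or both.
2. Count a steroid-only start as an outcome relapse only if the log book or chart shows that proteinuria returned after remission of proteinuria. Remission reached while still tapering should qualify, so that relapses during taper are kept.
3. Prespecify a repeat of the Objective 1 model with the three-day entry definition, counting the three days whether or not treatment has begun.

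Step 2 alone does not remove the contrast between the two physicians described above, because a promptly treated short rise still counts. Only step 3 tests that.

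The cost is one field on the form and one repeated model. Section 3.1 already provides for daily home urine logs and remission dates. Some promptly treated relapses with incomplete logs will be unclassified, and the three-day analysis may miss relapses that treatment clears before day 3. Fewer counted events also cost some power. If 1.68 per year includes both routes and 5%, 10% or 20% of relapses are steroid-only, dropping all of them gives about 90%, 88% or 84% power at 597 patients (570 / 0.95 = 600, 570 / 0.90 = 633 and 570 / 0.80 = 712 needed for 90%). No rule on when or how to treat changes.

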1.0 OVERVIEW

Nephrotic syndrome is the most common acquired kidney disease in children.¹ Affected children have recurrent episodes (or relapses) of proteinuria that may lead to life-threatening complications including sepsis, peritonitis and thromboembolism.² The goals of treatment are to induce remission of proteinuria, reduce the number of relapses, minimize toxicity of treatments and delay kidney damage.³ The first-line treatment for nephrotic syndrome is oral steroids, and many children will need repeated courses of steroids for relapsing disease.^{2,4} However, steroid treatment is associated with many side effects, including obesity, growth retardation, hypertension, cataracts, poor bone health, and cosmetic effects.^{2,5-15} Various other non-steroid immunosuppressive drugs are often used in the course of illness to decrease frequency of relapses and to avoid side effects of prolonged and recurrent steroid use.¹⁶ Treatment protocols for relapsing nephrotic syndrome are therefore complex, requiring multiple drugs and multiple courses of therapy over long periods of time for disease control.

International clinical practice guidelines are available to guide treatment of nephrotic syndrome;¹⁷ however, many of the recommendations are based on poor quality evidence and very few randomized controlled trials - leading to considerable debate among physicians regarding best treatment approaches.^{18,19} As a result, drug treatment protocols and processes of care for childhood nephrotic syndrome are highly variable among physicians and care centres; evidence practice gaps also exist.^{20,21} In a survey of Canadian pediatric nephrologists, we found striking variation in dose and duration of steroids and second line agents reportedly used for first presentation and relapses of nephrotic syndrome.²² Lack of consensus between physicians and centres regarding best treatment approach can lead to a frustrating experience for patients and families, poor satisfaction with clinical care, and sub-optimal outcomes.^{19,23} Using a priority setting survey, we identified that addressing these issues in the management of childhood nephrotic syndrome is the top priority for the Canadian pediatric nephrology community.

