The standard definitions used in nephrotic syndrome are provided in Appendix, Table 2. The data collection forms, shown in Appendix Figure 3, are designed to capture steroid prescriptions for each episode from the date of start of full dose steroid therapy (60 mg/m² or 2mg/kg) to cessation of steroid therapy or restart of full dose therapy. Each patient’s steroid prescription for an episode will be linked to the prescribing physician.

Data quality and standardization: Standardized case report forms will be used for data collection regarding the clinical course, outcomes and treatments for childhood nephrotic syndrome. All patient and physician data will be entered by study staff into a multi-centre online database (REDCap™, a web-application which allows users to build databases securely for the purposes of research and in particular for longitudinal cohort studies, <http://project-redcap.org/> hosted by Women and Children’s Research Institute, Edmonton, see letter from [name]). Data are being monitored weekly to address data quality issues in real-time. Based on the 77 subjects enrolled to date, we have confirmed that the majority of data to be collected for this study is recorded routinely by nursing staff in clinical care, and the web based system does not pose significant additional onerous data entry requirements.

The study will be coordinated centrally in Calgary. Two central study staff (study nurse and data analyst) will train all other site-specific study staff regarding study goals and objectives, data management and data entry. We put in place several measures to ensure data consistency and standardization including: piloting case report forms and standardizing forms; training site staff for data element definitions; using a data dictionary; establishing inter-rater reliability for data entry using two study staff at each site at start of study; and pre-study patient visit planning to standardize data collection and entry. Every 3 months, data analyst will review data entry completeness for individual patients and send reminders to appropriate site investigators for data completion. There will be a 2 step review for data completeness for each patient record – first by the data analyst and second by a lead investigator or designate. Data are time-stamped as complete after review. Key measures of data quality were identified a priori; a sample data quality report is attached in Appendix, Tables 3 and page 16.

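### A steroid course not started at full dose, given while the child is off steroids, forms no episode, although the relapse it treats can still be counted

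*Protocol*

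**What the plan says.** All references are to the protocol.

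- **Episode (3.1, Defining an episode of treatment).** An episode "is defined as the time from start of full dose steroid therapy" and runs "to cessation of steroids or re-start of full dose steroids as in steroid dependent patients who relapse while tapering steroids". Just before this, the same subsection uses the word differently: first presentation and "relapses of nephrotic syndrome (called ‘episodes’ in this study".
- **Data capture (3.1, next paragraph).** The forms "are designed to capture steroid prescriptions for each episode from the date of start of full dose steroid therapy".
- **Relapse at entry (3.1, Inclusion criteria).** It is "defined as proteinuria > 3+ on dipstick, > 3g/L on urinalysis or urine protein to creatinine ratio > 200 mg/mmol for 3 consecutive days", with no steroid condition.
- **Relapse in follow-up (3.1, Patient data being collected).** The proteinuria criteria must hold "for 3 consecutive days or start of full dose steroids". Either branch is enough.
- **Objective 1 (3.2).** The outcome counts relapses over person-time. The exposure is the total dose prescribed for episodes of proteinuria divided by days on steroids, and "Days on steroids is defined by the sum of the length in days of all episodes".
- **Objective 2 (3.3, Outcomes and Analysis plan).** The primary outcome is dose per episode, as a total and as a daily average. Episode length is secondary. The episode is the unit of analysis.
- **Objective 2 sample (3.3, Feasible sample and power considerations).** The 597 patients are expected to give up to 1015 episodes, counting the entry episode and a single further relapse in 70% of patients.

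**The concern.** Two definitions that should mesh do not. A relapse can be declared on urine findings alone, while an episode needs a particular steroid start. Between them lies the relapse of a child who is off steroids and is then treated with a course that does not begin at full dose.

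In Objective 1, exposure and outcome can then describe different sets of relapses within the same child. In Objective 2, a course enters the data only if its starting dose meets a threshold, and the outcome is the dose of that course. The study exists to explain variation in prescribing; section 1.0 reports of the investigators' own survey that "we found striking variation in dose and duration of steroids". An entry rule that depends on part of the prescription is a poor fit to that aim.

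**Working it through.** **1. The plan's own count.** Inputs from section 3.3: 597 patients, 70% with more than one episode.
597 + 0.70 × 597 = 597 + 417.9 = 1014.9, which reproduces 1015. The sum adds one episode for each further relapse. It is right only if every relapse is an episode, which the full-dose rule does not guarantee.

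**2. The definitions side by side, read literally.**

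| Situation | Counted as relapse? | Opens an episode? | Objective 1 exposure | Objective 2 |
|---|---|---|---|---|
| Off steroids, full dose started | Yes | Yes | Dose and days in | Observation |
| On taper, full dose restarted | Yes | Yes; the old one closes | Dose and days in | New observation |
| On taper, handled below full dose | Yes, on proteinuria | No | Dose and days stay in the running episode | No separate observation |
| Off steroids, course not started at full dose (nor later raised to it) | Yes, on proteinuria | No | Days out; dose unclear | Absent |
| No steroid prescribed | Yes, on proteinuria | No | No dose, no days | Absent |

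The fourth row is the defect. The third loses an observation but no dose.

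**3. What the fourth row does to the Objective 1 exposure.** Exposure = total dose ÷ days on steroids. The numerator refers to episodes of proteinuria and the denominator to defined episodes, so the dose of such a course may or may not enter.

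One-patient illustration, with assumed courses: one of 90 days started at full dose and averaging 30.64 mg/m² (the mean assumed in section 3.2), and one never at full dose, averaging 10 to 20 mg/m² over 30 to 60 days. The first contributes 30.64 × 90 = 2757.6 mg/m².

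- All steroid days counted: lowest (2757.6 + 10 × 60) ÷ 150 = 22.4; highest (2757.6 + 20 × 30) ÷ 120 = 28.0.
- Second course left out altogether: 30.64.
- Its dose in, its days out: lowest (2757.6 + 10 × 30) ÷ 90 = 34.0; highest (2757.6 + 20 × 60) ÷ 90 = 44.0.

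Under the last reading, adding a lower-dose course raises the recorded daily dose. A child with no full-dose start under observation has zero days on steroids, and the ratio is undefined. These figures show the mechanism in one child; they do not estimate a study effect.

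**4. Objective 2.** Total dose and average daily dose both contain the starting dose. Admitting a course only when that starting dose reaches the threshold is selection on a component of the outcome.

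**5. Size.** The protocol does not give the share of relapses treated by a separate course not started at full dose. As a conversion only: of the 1015 − 597 = 418 further relapses in the plan's count, an assumed share of 5% to 30% would be 21 to 125. Nothing in the protocol supports a value in that range over zero.

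**The case against.** The case on the other side is substantial, and much of it stands.

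- **A reader might infer that lower-dose treatment is removed from the dose analyses.** The protocol does not support that. An episode runs to the end of steroids or a full-dose restart, so every taper and any lower dose continuing after a full-dose start is included.
- **A reader might infer that low prescribers drop out and that variation between physicians and centres is understated.** Courses drop out, not physicians, whose full-dose-start courses remain. The survey sentence in 1.0 speaks of variable dose and duration. It does not say that treatment starts below full dose, and the only survey range given (2.4) is for duration, 7.5 to 26 weeks.
- **A reader might try to size the effect by cutting the lower tail off the dose distribution in 3.2 (SD 8.85).** That SD belongs to mean daily dose, whereas the rule acts on starting dose. With assumed courses, 60 mg/m² for 14 days and then an average of 10 for 76 days gives (840 + 760) ÷ 90 = 17.8 per day and is included. A course of 40 for 14 days gives 40 per day and is excluded. Even the direction of a shift in the mean is not fixed.
- **Much of the information may be collected anyway.** The beginning and end of all relapses are study points, and log books record steroid dose given. This helps recovery, but no stated rule carries those doses into the analyses, and the forms are described as starting at the full-dose date.
- **Appendix Table 2 and Appendix Figures 3 and 4 may reconcile the terms.** They are not available here. The body text would still conflict with itself.
- **A treatment-defined unit is defensible for a prescribing question.** It is, but that does not require the treatment to begin at a given dose.

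**Conclusion.** The point holds for one group: separate steroid courses not started at full dose, given to a child off steroids for a relapse that qualifies on proteinuria. Followed as written, such a relapse adds to the Objective 1 outcome without its days, with the treatment of its dose ambiguous, and its course is missing from Objective 2. The 1015 figure rests on equating relapse with episode.

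This assumes that the relapses counted in 3.2 are those defined in 3.1, the only definition given for follow-up. Because the share affected is unknown, the effect may be negligible; equally, forms built on the full-dose date may not allow the investigators to show that. Confidence is medium. The definition should be changed, since the stated rule gives a worse data set than an inexpensive alternative.

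**What to change.** Reconcile the relapse and episode definitions in 3.1 (Inclusion criteria, Patient data being collected, Defining an episode of treatment, and the description of the forms), the exposure in 3.2 and the episode count in 3.3. For analysis:

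1. Let any steroid course prescribed for a counted relapse open an episode, whatever its starting dose, and flag whether it began at full dose.
2. Put the dose and the days of each such course into both parts of the Objective 1 ratio.
3. Record a relapse with no steroid prescribed as zero total dose, leave it out of average daily dose and of length (both would rest on zero days), and report how many there are.
4. State how a relapse within a running course is handled, so that running courses are not split unintentionally.
5. Report full-dose-start episodes alone as a sensitivity analysis.

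The cost is a small change to the episode form and data dictionary, as relapse starts and ends are already study points, plus a chart check for the 77 patients already enrolled. This concerns the data definition only; no dose or treatment rule is recommended.
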